#### Secondary:

### A Fisher's exact test or Chi-square test will be used to compare the usage of screw fixation between the Tritanium® Acetabular Shell and Trident® X3® Polyethylene Insert studies. If there are any statistically significant differences in baseline variables (e.g. age, gender, diagnosis) between the groups, they will be addressed as covariates and ANOVA or ANCOVA will be used.

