#### 3.3 Number of Subjects

Cases will be enrolled in this study until a total of 240 receive the Tritanium® Acetabular Shell. Half of these cases will use the X3® polyethylene insert alone as the bearing surface; the other half will use the MDMTM liner coupled with a compatible ADM/MDMTM X3® insert as the bearing surface. These treatment groups will not be separated into arms; instead, investigators will use their clinical judgement in determining the appropriate bearing for each case. If enrollment in one of the treatment groups begins to outpace that of the other, centers may be asked to enroll only those cases that are candidates for the bearing surface for which enrollment is lagging. Following this plan, cases will not be artificially placed into a treatment group to which they may not be best suited on the basis of the timing of their enrollment; consequently, there will be fewer opportunities for protocol deviations with regard to treatment.

Only the following ancillary devices may be used according to this study protocol:

- Stryker X3® polyethylene inserts (120 cases)
- Stryker MDMTM liners with ADM/MDMTM X3® polyethylene inserts (120 cases)
- Stryker LFIT™ CoCr heads or BIOLOX delta or alumina ceramic heads (in cases where the MDM™ liner is used, only 22.2 mm and 28 mm heads are permissible)
- Stryker Universal Adapter Sleeves (for use with BIOLOX delta universal ceramic heads)
- Compatible Stryker femoral stems
- Stryker Orthopaedics Torx Bone Screws

The Tritanium® Acetabular Shell is described in detail in Section 6 of this protocol, Device Description.

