### 9.1.2 Secondary Efficacy Parameters

The secondary efficacy parameters include:

- The usage of screw fixation
- HHS at the 1-, 3- and 5-year follow-up visits
- SF-12 scores at the 1-, 3- and 5-year follow-up visits
- LEAS at the 1-, 3- and 5-year follow-up visits
- EQ-5D at the 1-, 2-, 3-, 4- and 5-year follow-up visits
- Follow-Up Questionnaire annually in postoperative years 6-10

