### 9.1.5 Secondary Efficacy Analysis

A two-sided 0.05 alpha level will be used.

For comparison of usage of bone screw fixation between the Tritanium® Primary Acetabular Shell Study and the Trident® X3® Polyethylene Insert Study, a Chi-square test or Fisher's exact test will be used. If there are any statistically significant differences in baseline variables (e.g. age, gender, diagnosis) between the groups, they will be addressed as covariates and ANOVA or ANCOVA will be used.

For comparison of HHS, and SF-12 and LEAS at 1, 3 and 5 years postoperative between the Tritanium® Acetabular Shell and Trident® X3® Polyethylene Insert studies, a t-test or Wilcoxon test will be used. If there are any statistically significant differences in baseline variables (e.g. age, gender, diagnosis) between the groups, they will be addressed as covariates and ANOVA or ANCOVA will be used.

EQ-5D values and changes from baseline will be presented for each interval. Data from the Follow-Up Questionnaire will be used as an input to the Kaplan-Meier survival curve for postoperative years 6-10; any adverse events collected via the Follow-Up

Questionnaire will be reported on a separate Adverse Event eCRF and included in the safety analysis.

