## SURGICAL DETAILS

Submit Surgical Details CRF ONLY if surgery is performed and subject receives study device.

GENERAL INFORMATION					
SUBJECT	INITIALS:	SURG	GERY DATE:	SUBJECT ID:	
	The state of the s				
I SUBCICAL DETAILS		(DC	D-MMM-YYYY)		S. St. Phys.
I. SURGICAL DETAILS	D. MALICOLE I	DEDAID OD			
A. APPROACH  Anterior	B. MUSCLE I		REATTACHMENT REQUIR		TION USED?
Anterolateral	O No		which muscle group?	○ Yes	
O Posterior/ Posterola		A CHARLES TO COL	rnal Rotators eus Medius	○ No	
O Dual Incision	iteral	Othe	and the state of t		
() Lateral		_ othe			
D. INCISION LENGTH					
	E. DURATIO			F. ESTIMA	TED BLOOD LOSS
cm	Skin to Ski	n	minutes		cc
I. PROSTHESES					
G. PROSTHESES - Upload a copy of the con	nnonent lahel/s) implant	her	H. OTHER?	O Yes* O N	No
Acetabular Shell -	inponent tabel(s) implant		*If Yes, specify an	d upload a copy of the la	bel(s).
Go to Subject Informatio	n screen and enter data	in Products	tab. Add Row Other (S	Specify) Reference #	Lot#
	Reference #	Lot#	Reset	Specify) Reference #	LOT#
Acetabular Liner		II Nowe	×		
Acetabular Insert	Reference #	Lot#	Attitude (S.V.)	NAME OF TAXABLE PARTY.	
Acctabalal Insert	Reference #	Lot#			
Femoral Bearing Head	- HOIGIGING II	2001			
	Reference #	Lot#			
Femoral Stem					
I. BONE SCREWS USED?	○ Yes* ○ No				
*If Yes, specify and uploa					
Add Pow					
Reset	e# Lot:	#	J. INTRAOPERATIVE	COMPLICATION?	
X				E form. (a) Yes* (	No
				0	
			K. DISCHARGED TO:	: (Check One)	
			Skilled Nursing Fa	cility	
			Chronic Care Cent	ter	
			Rehabilitation Un	it	
			O Home		
			the Electric transfer of the second		
			Other: (Specify)		
			Discharge Date:		
I. COMMENTS				DD-MMM-YYYY	
II. COMMENTS					
	Reason for Save				
Verification / Cor	nfirmation Method				
			Cubacia		
0Aug2011 Ver 1 0			Submit		
9Aug2011 Ver.1.0		Pa	age 1 of 1		

[figure not shown]

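### Screw usage is a Yes/No outcome, yet its covariate-adjusted comparison is planned by ANOVA or ANCOVA, so the standard error may be too small or too large when group sizes and usage rates both differ

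*Combined protocol and SAP*

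**What the plan says.** Section 9.1.2 lists "The usage of screw fixation" among the secondary efficacy parameters. The Surgical Details form in Appendix E records it under "BONE SCREWS USED" with a Yes or No answer.

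Section 9.1.5 sets the level for the secondary analyses: "A two-sided 0.05 alpha level will be used". For screw usage it says that "a Chi-square test or Fisher's exact test will be used". It then adds that, if any baseline variable (age, gender and diagnosis are the examples) differs significantly between the groups, "they will be addressed as covariates and ANOVA or ANCOVA will be used".

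The Statistical Methodology part of the synopsis gives the same plan. It opens with "A Fisher's exact test or Chi-square test will be used to compare the usage of screw fixation" and ends with the same ANOVA/ANCOVA sentence. Both places attach that sentence also to the HHS, SF-12 and LEAS comparison, where the outcomes are scores. Neither the statistical plan nor the synopsis names a logistic or other binary-outcome model, or a robust standard error.

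**The concern.** The unadjusted test suits a proportion. The adjusted one is a normal-theory linear model with a single residual variance for both studies. For a Yes/No outcome the variance is p(1 − p), so it differs between studies when usage differs. A pooled standard error weights the two variances by the wrong sample sizes unless the groups are equally large. A linear model can also give fitted usage below 0% or above 100% when usage is near a limit.

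The adjusted route is a realistic one. The comparison is with a historical control in a non-randomised study, and any single significant baseline difference triggers it. Even with no true differences, testing k independent baseline variables at 5% (an assumption; the plan does not state the level or number of these tests) triggers it with probability 1 − 0.95^k: 14% for k = 3, 23% for k = 5 and 40% for k = 10.

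At stake is the precision attached to the adjusted usage difference, and so how firmly the report can say that screw use differs from the earlier shell.

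**Working it through.** The plan gives no rate, sample size, power or standard error for screw usage, so there is no figure of its own to reproduce. The 142 and 177 cases in section 9.4.2 concern the primary endpoint and do not bear on this point.

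**Inputs**
- Study hips: n1 = 240, from section 3.3 ("Cases will be enrolled in this study until a total of 240 receive the Tritanium® Acetabular Shell"). The synopsis objective speaks of cluster-hole procedures, and solid-back shells are also allowed, so the true denominator may be smaller.
- Control hips: n2 is not given. Assumed 80 to 480.
- Usage: not given. Assumed p1 = 10% in the study and p2 = 40% in the control.

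**Formulas, without covariates**
- Within-group variances: v1 = 0.10 × 0.90 = 0.09; v2 = 0.40 × 0.60 = 0.24.
- Common variance used by ANOVA: v = (n1·v1 + n2·v2)/(n1 + n2). This is the average within-group variance, not the variance at the pooled proportion.
- ANOVA standard error: √[v(1/n1 + 1/n2)].
- Correct standard error: √(v1/n1 + v2/n2).
- Actual coverage of a nominal 95% interval: 2Φ(1.96 × ratio) − 1.

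**Worked case, n2 = 120**
- v = (240 × 0.09 + 120 × 0.24)/360 = 50.4/360 = 0.14.
- ANOVA: √(0.14 × 0.0125) = √0.00175 = 0.0418.
- Correct: √(0.000375 + 0.002) = √0.002375 = 0.0487.
- Ratio: 0.0418/0.0487 = 0.858.

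| Control hips | Common variance | ANOVA SE | Correct SE | Ratio | Coverage |
|---|---|---|---|---|---|
| 80 | 0.1275 | 0.0461 | 0.0581 | 0.79 | about 88% |
| 120 | 0.14 | 0.0418 | 0.0487 | 0.86 | about 91% |
| 240 | 0.165 | 0.0371 | 0.0371 | 1.00 | 95% |
| 480 | 0.19 | 0.0345 | 0.0296 | 1.17 | about 98% |

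**Direction.** The error reverses if the rates are swapped. With 40% in the study, 10% in the control and 120 controls, v = (240 × 0.24 + 120 × 0.09)/360 = 0.19, and the ratio is √0.002375/√0.00175 = 1.17.

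**Denominator.** The ratio depends only on n2/n1. If cluster-hole shells made up 120 of the 240 cases (assumed), 240 controls would give a size ratio of 2. At 10% v 40% the result would be 1.17, not 1.00.

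**Wider range.** Over assumed rate pairs between 5% and 50%, and 80 to 480 controls, the ratio runs from 0.71 to 1.42. It is exactly 1.00 when rates are equal or when n2 = 240.

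**With covariates.** These figures come from simulation, 3,000 runs per scenario, with a logistic truth and a baseline covariate shifted 0.3 to 0.5 SD between studies.
- ANCOVA standard error over the empirical SD: 0.91–1.18 with 120 controls, 0.99–1.01 with 240, and 0.85–1.11 with 480.
- ANCOVA over all scenarios: coverage 89.8%–98.1%; type I error 3.0%–6.5%.
- Same linear model with an HC3 robust standard error: coverage 94.3%–95.4%; type I error 4.3%–5.4%.
- Logistic regression: type I error 3.4%–5.5%.

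**The case against.** The strongest reply is that, as a test, the planned method is close to adequate. Without covariates, Pearson's chi-square equals N × R² from the linear model on the 0/1 outcome, so the ANOVA test is a monotone function of the test the plan uses first. With covariates and equal usage, its size was 3.0%–6.5% in simulation, little worse than logistic regression. Section 9.1.5 promises a comparison at 0.05 and no interval for screw usage; the plan promises intervals only for the primary endpoint and adverse-event rates. This stands, and it limits the harm mainly to the reported precision of the difference.

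A second reply is that the ANCOVA sentence is identical to the one for the continuous scores and may simply have been carried over. That may explain it, but it leaves the wrong method in force. The surgical form also has a row for each screw, so a count could be derived. However, the chi-square or Fisher choice, and the synopsis objective's reference to rates, show that the planned endpoint is a proportion.

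A reader might infer more than the documents support:
- **That the standard error is wrong whenever usage differs.** It is not: with equal group sizes the ratio is 1.00 without covariates and within about 1% with them.
- **That the adjusted estimate is biased or power is lost.** Neither was calculated, and nothing here establishes either.
- **That adjustment is near certain because the two studies lie years apart.** The documents call the control historical but give no dates.

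**Conclusion.** The point holds in a limited form. The plan names a constant-variance linear model as the adjusted analysis of a Yes/No outcome, in two places, and nothing elsewhere corrects it. The standard error may then be too small or too large when group sizes and usage rates both differ. With covariates in the model, unequal sizes and a covariate that shifts the variance can also move it somewhat.

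The size cannot be fixed from the documents. The illustrated ratios of 0.86, 1.00 and 1.17 rest on assumed rates of 10% and 40%, on assumed control sizes, on all 240 hips counting, and on no covariates. Nothing in the plan makes the two groups equal in size, so the favourable case cannot be presumed.

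This is a conditional fallback for one secondary endpoint. Its place at the head of the list in section 9.1.2 gives it no formal priority. It merits correction because a better method is available at almost no cost, not because the trial's main conclusion is at risk.

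**What to change.** In section 9.1.5 and in the synopsis, separate the screw-usage sentence from the one for the scores. For screw usage, replace ANOVA or ANCOVA with logistic regression on study and the baseline covariates, and report the covariate-standardised risk difference with a 95% confidence interval. A linear model on the 0/1 outcome with robust standard errors is an equally valid cure for the variance problem; the plan should name one of the two in advance. Keep ANCOVA for HHS, SF-12 and LEAS.

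The cost is one sentence in two places. No new data are needed, and neither the sample size nor the primary analysis changes.

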#### Clinical Outcomes:

Clinical outcomes will be evaluated via the total HHS, including pain, motion and function, preoperatively and at the 6-week, 1, 3, and 5-year visits. Additional HHS data will be obtained at the 7-year and 10-year time points at investigational sites that choose to bring their subjects back in for these optional visits.

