#### 7.4 Annual Follow-up Visits

Clinical data will be collected via office visit by the investigator at the following annual postoperative intervals: 1-year, 3-year and 5-year. Tools for postoperative evaluation will be the HHS, AP hip, AP pelvis and lateral radiographs.

Patient outcomes data will also be collected via patient questionnaires. At each of the 1-year, 3-year and 5-year follow-up visits, the SF-12, LEAS and EQ-5D are required. These same questionnaires are also required at 2-year and 4-year intervals, and may be completed during an office visit or sent to the subject to be completed, initialed and dated and returned to the investigative site.

All clinical data, radiographs, and patient outcomes data must be collected within  $\pm$  2 months of the 1-year and 2-year anniversary dates. For remaining annual time points, the window expands to  $\pm$  3 months of the 3-year anniversary date and  $\pm$  4 months of the 4-year and 5-year anniversary dates.

The initial phase of the study will continue for 5 years after surgery and include collection of the previously described radiographs, HHS, and SF-12, LEAS and EQ-5D patient questionnaires. In the second phase of the study, all subjects will complete a brief satisfaction questionnaire annually at the 6-year, 7-year, 8-year, 9-year and 10-year follow-up intervals. This form may be completed by the SC during a patient telephone interview, or by the patient either at home or during a clinic visit. The questionnaire will be used to obtain the following information, at a minimum:

- Patient satisfaction with the hip replacement
- Presence of any pain in the study hip
- Any surgeries performed on the study hip

The questionnaire will also provide information on any revisions and enable calculation of the Kaplan-Meier survival curve necessary to meet the primary endpoint of the study.

Additionally, at investigational sites that choose to continue collecting clinical and radiographic data during the second phase of the study, subjects will be evaluated again at 7 and 10 years after surgery.

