### 9.3 Missing Data

No missing data will be imputed for the primary analysis and secondary analyses.

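### HHS, SF-12 and LEAS are compared with the historical control by separate tests at 1, 3 and 5 years in 5-year-evaluable cases only, and the required year-2 and year-4 scores enter no named comparison

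*Combined protocol and SAP*

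**What the plan says.** Section 9.1.5 gives the method "For comparison of HHS, and SF-12 and LEAS at 1, 3 and 5 years postoperative": a t-test or Wilcoxon test between the study and the Trident X3 historical control, with ANOVA or ANCOVA if baseline variables differ significantly. The level is stated as "A two-sided 0.05 alpha level will be used". The Synopsis adds that HHS, SF-12 and LEAS are compared as improvement from the preoperative score. No repeated-measures model appears anywhere, and section 9.3 states: "No missing data will be imputed for the primary analysis and secondary analyses".

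Collection is wider than analysis. Of SF-12, LEAS and EQ-5D, section 7.4 says: "These same questionnaires are also required at 2-year and 4-year intervals". Section 9.1.2 then lists "SF-12 scores at the 1-, 3- and 5-year follow-up visits" and "LEAS at the 1-, 3- and 5-year follow-up visits", while for EQ-5D it lists "EQ-5D at the 1-, 2-, 3-, 4- and 5-year follow-up visits". HHS is different: section 2.1.2 collects it "preoperatively and at the 6-week, 1, 3, and 5-year visits", so it has no year-2 or year-4 value.

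Section 9.4.4.1 bases both primary and secondary efficacy on the per protocol population, which leaves out cases unavailable at the 5-year primary endpoint. Section 9.4.2 allows for 20% loss within 5 years.

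**The concern.** Two features combine. First, eligibility for the 1- and 3-year tests depends on something that happens later, namely being evaluable at year 5. A patient with a poor 1-year score who leaves in year 2 is removed from the 1-year comparison although the score was recorded. Second, the scores that say most about a missing 3- or 5-year value, those a year earlier, are collected for SF-12 and LEAS but not used in the comparison. Section 7.4 lets the year-2 and year-4 forms be returned without an office visit, so they may exist for patients who do not attend the clinic.

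If patients who are doing badly are likelier to leave, the remaining cases look better than the implanted group. These comparisons carry the plan's claim that pain, function and quality of life are comparable to the predicate shell, so a shift in one group's mean matters even though the endpoints are secondary.

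**Working it through.** **The plan's own figure.** The only sample size in the plan is for revision. With p0 = 0.94, p1 = 0.99, one-sided alpha 0.05 and power 0.95:

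n = [(1.645·√(0.94·0.06) + 1.645·√(0.99·0.01)) / 0.05]² = 122.9

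The continuity correction gives (122.9/4)·[1 + √(1 + 2/(122.9·0.05))]² = 142.2, against the stated 142. Then 142/0.8 = 177.5, stated as 177. No sample size is given for HHS, SF-12 or LEAS. What carries over is the 20% loss: of 240 cases, 48 are lost and 192 remain.

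**Assumed inputs (not in the documents).** Simulation A used 800 trials per setting, five yearly visits, within-person correlation 0.6 to 0.8, 17% to 23% missing at year 5, and log-odds of dropout rising by 0.5 or 1 per SD worse last score (odds ratio 1.6 or 2.7). Simulation B used 1,500 trials of 240 cases, SD 10, base correlation 0.5 or 0.7 decaying with lag, preoperative, 6-week and yearly visits, 20% loss by year 5, and log-odds rising by 1 per SD.

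**Bias in the 5-year mean with observed scores only.** Simulation A gives 0.056–0.068 SD for the weaker dropout and 0.131–0.154 SD for the stronger. Simulation B gives 0.84–1.20 points, or 0.08–0.12 SD, when dropout depends on the last recorded score. For scale, the standard error of a mean of 192 cases is 10/√192 = 0.72 points, so this bias is 1.2 to 1.7 standard errors of the study group's own mean. With random dropout the bias is zero.

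**Effect of the 5-year restriction on earlier visits** (simulation B, dropout on recorded scores, points on SD 10):

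| Visit | All who returned at that visit | 5-year-evaluable cases only |
|---|---|---|
| 1 year | 0.21–0.28 | 1.13–1.39 |
| 3 years | 0.53–0.78 | 1.11–1.40 |

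**Share of the 5-year bias removed by a likelihood-based repeated-measures model on all implanted cases** (simulation B):

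| Dropout depends on | Bias, observed only | Pre-op, 6 weeks, years 1–5 | HHS schedule (pre-op, 6 weeks, years 1, 3, 5) | Pre-op, years 1–5, no 6-week visit |
|---|---|---|---|---|
| Last recorded score | 0.84–1.20 | about 100% | 85–87% | 84–86% |
| Half and half | 0.96–1.30 | 71–79% | 60–70% | 59–67% |
| Unseen current score | 1.09–1.33 | 49–65% | 44–61% | 41–55% |

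Comparing the third and fourth columns shows what years 2 and 4 add once the 6-week visit is in the model: from 85–87% to about 100% in the first row, but only from 44–61% to 49–65% in the last.

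**The same model inside the per protocol set.** If every included case has a year-5 score, the likelihood estimate of the year-5 mean is the sample mean of those cases. Earlier visits cannot move it, so 0% of the bias is removed in every scenario (0.84 stays 0.84 and 1.20 stays 1.20). This needs no assumption about correlation or dropout. It does take evaluable at 5 years to mean that a 5-year score was recorded.

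**The case against.** The strongest points against are these.

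- *The control may share the bias.* The planned quantity is a between-study difference. A reader might infer that the control's dropout differs, so that the bias does not cancel. The documents do not support that: they give no control size, dropout or missing-data pattern, and the Synopsis says only that its intervals and data closely match. Similar dropout would cancel much of the bias. This stands, and it leaves the net bias unknown rather than zero.
- *Dropout may be unrelated to scores.* The attrition cause named in section 15.3 is loss of insurance, with reimbursement to limit it, and 20% is an allowance made for the revision endpoint rather than a forecast of missing scores. This also stands; the direction and strength are assumed.
- *Years 2 and 4 may be used elsewhere.* A reader might infer that those scores enter no analysis at all. Section 2.1.2 promises comparison with preoperative status and section 9.4.1 promises descriptive tables, and neither excludes them. What can be said is that no between-study comparison names them.
- *The model has its own assumptions.* LEAS is ordinal, and HHS can sit near its ceiling (97.0 ± 6.2 with maximum 100 in the published series cited in section 1.1), so Wilcoxon has a place. It belongs in the sensitivity analysis.
- *Years 1, 3 and 5 are prespecified consistently, for unpowered secondary endpoints.* True, but the proposed model still reports those three contrasts.

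**Conclusion.** The concern holds for the selection of cases and the unused SF-12 and LEAS scores. The size, about 0.06 to 0.15 SD in the study group's 5-year mean, is conditional on about 20% loss, the assumed correlations and dropout driven by earlier recorded scores. It describes one group's mean score, not the study-minus-control difference.

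Two stronger readings are tempting and should not be adopted. One is that each test uses whoever returned at that visit; section 9.4.4.1 rules this out for years 1 and 3, where the selection is stricter and, in the simulation, more biasing. The other is that a mixed model would remove most of the dropout bias whatever the cause. It removes none inside the per protocol set, and with all implanted cases the share depends on a dropout mechanism that the documents do not reveal. For HHS the argument about years 2 and 4 does not apply.

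This is an inexpensive improvement to secondary analyses and does not touch the revision endpoint.

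**What to change.** 1. In section 9.1.5, make the main analysis one mixed model for repeated measures per score, with study, visit, study-by-visit, baseline score and any baseline covariates found to differ, and unstructured covariance. Use every scheduled postoperative visit common to both studies (for HHS, at most 6 weeks and years 1, 3 and 5). Report the study difference at 1, 3 and 5 years with 95% confidence intervals.
2. In section 9.4.4.1, define the population for these score analyses as all implanted cases with a baseline and at least one postoperative score. Step 1 does not correct the 5-year bias without this.
3. State how scores after shell revision are treated. Section 10.3 ends participation at revision, so the model would implicitly predict unrevised-type scores. At the assumed 99% success this concerns about 240 × 0.01 = 2.4 cases, but the estimand should be explicit.
4. Keep the per-visit t-test or Wilcoxon test in the per protocol set as a sensitivity analysis, and add a delta-adjusted analysis for dropout that depends on unseen scores.
5. Section 9.3 can stand for the main model, which imputes nothing. If the delta-adjusted analysis is done by imputation, it needs a stated exception.

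The cost is plan wording and modest programming on data already required of study subjects. Individual control data are needed, as ANCOVA and Wilcoxon already imply. The downside is reliance on a normal model and on missingness explained by recorded scores, which the two sensitivity analyses probe.
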